10.7 Other safety measurements

Other safety measurements will include physical examinations, vital signs, 12-lead ECGs, and assessment of suicidality.

If deemed necessary by the Investigator, eg, in case of a suspicious AE, the Investigator can initiate additional/unscheduled laboratory testing, vital signs, ECGs, or other assessments for safety evaluation during the study.

10.7.1 Physical examination

Full physical examinations will be performed at the time points specified in Table 5-1. Full physical examinations will include cardiac and respiratory function via auscultation and review of the following body systems: general appearance; ear, nose, and throat; eyes; hair and skin; respiratory; cardiovascular; gastrointestinal; musculoskeletal; hepatic; neurological; and mental status.

Height (study participant without shoes, and height rounded to the nearest 0.5cm) and body weight (study participant in underwear or light clothing, without shoes and rounded to the nearest 0.1kg) will be recorded at the Screening Visit and BMI will be derived (weight (kg)/ [height (m)]²).

Vital signs

his docuration vit Vital signs (PR, RR, SBP, DBP, and oral temperature) will be recorded at the time points shown in Table 5-1.

For the purposes of assessing the inclusion criterion, at the Screening Visit and the Baseline Visit, BP measurements will be performed in both supine and standing positions according to the following procedure: Measure supine BP after the study participant has been lying down for 10 minutes, then ask the study participant to stand up and record the standing BP variations thereof. after 1 minute and 3 minutes. At all time points after the Baseline Visit, BP will only be measured in the supine position, ie, there will be no assessment for orthostatic hypotension.

By decision of the sponsor and the Investigator, the time points specified in Table 5-1 may be modified based on preliminary safety and PK assessments from previous doses tested in the study.

10.7.3 Standard 12-lead ECG

Triplicate standard 12-lead ECGs (RR interval, PR interval, QRS interval, QT, QTcB, and QTcF) will be recorded at times specified in Table 5-1, according to the following procedure: study participant lies in a supine position for >5 minutes; then a 12-lead ECG wilk be recorded in the same position. All ECG recordings will be performed in triplicate at 2- to 3 minute intervals.

Electrocardiograms will be recorded at a speed of 25mm/s and with a calibration of 1cm/mV.

The purpose of the enhanced ECG monitoring procedures in this study is to match the observed ECG parameters with the contemporaneous plasma levels of PSL as closely as possible, at key time points during Day -1 (no exposure) and Day 8 (anticipated peak exposure). This will support an evaluation of any relationship between exposure to PSL and changes in key ECG parameters, most particularly QT intervals.

As specified in Table 5-1, a Baseline ECG series will be performed on Day -1. On this day, triplicate standard 12-lead ECGs will be performed for each of the following time points, intended to match as closely as possible the timing of the PK sampling series planned for Day 8: 0h, 30min, 1h, 2h, 3h, 6h and the pre-evening dose PK sample. On Day 8, a matching series of ECGs will be performed predose, 30min, 1h, 2h, 3h, and 6h after the morning dose of PSL, and approximately 30min before the evening dose, as close as possible to the time of the pre-evening dose PK sample. On Day 1 through Day 12, except Day 8, the triplicate standard 12-lead ECG will be performed prior to the morning dose of PSL, again timed to match as closely as possible to the time of the predose PK sample being taken. Care should be taken to record the timing of each ECG and PK sample as accurately as possible, to enable the precise evaluation of their temporal relationship.

By decision of the sponsor and the Investigator, the time points specified in Table 5-1 may be modified based on preliminary safety and PK assessments from the study.

The Investigator or designee will determine whether the results of the ECG are normal or abnormal. All important abnormalities should be reported. The original ECG tracing will be signed or initialed, and dated by the Investigator or designee, and will be retained at the clinical site as part of the Investigator's Site File. The original electronic file of all ECG tracings will be his documents transferred to UCB on completion of the study, or earlier, if required.

Assessment of suicidality

The C-SSRS will be completed at the scheduled time points presented in Table 5-1.

Suicidality will be assessed by trained study personnel using the C-SSRS (Posner et al, 2011). This scale will be used for screening as well as to assess suicidal ideation and behavior that may occur during the study. The Investigator's decision about study participant continuation in the

study or study participant withdrawal from the study if the study participant has a positive response to the CSSRS Question 4, should be based on the benefit/risk balance for continuation or discontinuation of study treatment in view of the individual study participant circumstances,

Las management options, etc. In an additional visit (or unscheduled visit) is conducted due to safety or efficacy reasons, a C-SSRS assessment will be performed with the study participant during the visit. If an additional visit (or unscheduled visit) is conducted for reasons other than safety or efficacy concerns (eg, replacement of lost medication, repeated collection of a laboratory specimen due to collection or analysis issues), a C-SSRS will not be required at these visits. Details of the case must be documented by the Investigation staff conductive the Table Staff cond

staff conducting the C-SSRS) and provided to UCB via the SAE reporting process

STUDY MANAGEMENT AND ADMINISTRATION 11

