7.2 Treatment to be administered

Padsevonil will be administered orally with 8oz (240mL) water, 30 minutes after a light or standard meal for the morning dose and 30 minutes after a standard meal for the evening dose, according to Table 7-1.

Day	Morning dose	Evening dose
1 (Til)	100mg	100mg
2 (Ti2)	200mg	200mg
3 (Ti3)	200mg	200mg
4-7 (M1-M4)	400mg	400mg
8 (M5/Tal)	400mg	200mg
9 (Ta2)	200mg	200mg
10 (Ta3)	200mg	200mg
11 (Ta4)	100mg	100mg
12 (Ta5)	100mg	100mg

Padsevonil administration Table 7-1:

M=Maintenance; Ta=Taper; Ti=Titration

Treatments will be administered in an open-label fashion. Study participants will continue to take This docu OXC, LTG, LEV, or BRV as per their usual regimen.

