7.8.4 Diet, fluid, and activity control

During the Preatment Period, study participants will complete a light meal 30min prior to each morning dose of IMP, and a standard meal 30min prior to each evening dose of IMP.

Study participants should keep their usual diet (besides the restrictions for the study) necessary for the maintenance of good health; excessive food consumption should be avoided. Study participants should refrain from heavy physical exertion (eg, vigorous exercise) from 3 days prior to (first) confinement and during the study.

his docut Study participants should not consume more than 3 units alcohol/day (females) and 4 units alcohol/day (males), or more than 600mg of caffeine/day (200mL of coffee contains approximately 100mg of caffeine, 200mL of black tea approximately 30mg, and 200mL of cola approximately 20mg) from 48 hours prior to each administration of PSL and until the final PK plasma sampling of the Treatment Period.

Grapefruit, starfruit, and pawpaw (as beverage, fruit, or supplements) within 72 hours before first

Study participants must refrain from donating blood or plasma during the course of the study in the study.

Water will be available ad libitum except for between 1 hour before and 2 hours after dosing. A total of 240mL of water will be given to each study participant at the time of administration of Ji tion and any IMP.

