8.1.2 Baseline Visit (Day -1)

sions or variations thereof. Study participants will check in to the unit on the afternoon prior to this visit and will be assigned their Study Participant Identification Card. The following procedures/assessments will plication and be performed before discharge:

- Inclusion/exclusion criteria verification
- General medical/procedures history
- Enrollment to Inducers or Neutral (control) Group
- Dispense Study Participant Identification Card •
- C-SSRS ("Baseline/Screening" version of the C+SSRS) • autho
- Full physical examination •
- Prior and concomitant medications •
- Vital signs (including PR, RR, SBP, DBP, and oral temperature)
- **Triplicate 12-lead ECGs**
 - Morning: approximately 0.5h prior to the expected time of the morning dose on Day 8, and 0.5h, 1h, 2h, 3h, and 6h after the expected time of the morning dose on Day 8
 - Evening: approximately 0.5h prior to the expected time of the evening dose on Day 8
- Blood samples (venous) for trough PK analysis (prior to AED morning dose):
 - MHD plasma level (only for study participants taking OXC)
 - AED trough level (for storage)
- Blood and urine samples for the following clinical laboratory tests will be collected:
 - Hematology, serum chemistry, and urinalysis
 - Urine pregnancy test (for women of childbearing potential only)
 - Urine drug screen
- Alcohol breath test
- Recording of AEs/medical procedures

there of.

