hisdoci

will be administered at the Screening Visit. A urine pregnancy test will be administered at Baseline and the EOS Visit.

wailations thereof Laboratory safety measurements will be performed after a fasting period of at least 4 hours only at the Screening Visit. Clinical laboratory parameters to be measured are presented in Table 10-2.

Sampling time and last AED intake should be recorded in the eCRF.

Table 10-2:	Laboratory measurements
-------------	-------------------------

Hematology	Hemoglobin, hematocrit, red blood cell count, mean corpuscular volume, platelets, total white blood cell count, and differential consisting of absolute counts and percentages of the following leukocyte types: neutrophils, lymphocytes, monocytes, eosinophils, and basophils
Serum chemistry	Sodium, potassium, calcium, inorganic phosphorus, fasting glucose, urea, creatinine, total bilirubin (conjugated bilirubin when total bilirubin is outside the reference range), total protein, albumin, ALT, AST, and ALP
Viral serology (only at Screening Visit)	HIV-1/2Ab, HBsAg, and HCV-Ab
Pregnancy	Serum pregnancy test at the Screening Visit
Hormone tests	Follicle-stimulating hormone (at Screening only to confirm postmenopausal status in female study participants)
Urinalysis	Specific gravity, pH, glucose, protein, blood, leukocytes, nitrite, ketones, bilirubin, urobilinogen (with dipstick) If protein or blood or leukocytes are abnormal (positive), a microscopic examination of the sediment will be performed.
Drug screen	Amphetamines/methamphetamines, benzodiazepines, barbiturates, cocaine, cannabis, methadone, tricyclic antidepressants, and opiates

ALT=alanine aminotransferase; ACP=alkaline phosphatase; AST=aspartate aminotransferase; HBsAg=hepatitis B surface antigen; HCV-Ab=hepatitis C antibody; HIV-1/2Ab=human immunodeficiency virus-1/2 antibodies

Evaluation of PDILI 10.6.1

The PDILI IMP discontinuation criteria for this study are provided in Section 6.4.3, with the accompanying required follow-up investigation and monitoring detailed below. All PDILI events must be reported as an AE and reported to the study site and sponsor within 24 hours of learning of their occurrence. Any PDILI event that meets the criterion for potential Hy's Law must be reported as an AE of special interest (see Section 10.1.1.3), and, if applicable, also reported as an SAE (see Section 10.1.1.2).

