12.4.3 Vital signs and ECGs

Vital sign variables (PR, RR, SBP, and DBP) and changes from Baseline (predose on Day 1) will be summarized at each time point by group. Frequency tables of values outside the normal ranges will be produced by treatment group and time point.

Electrocardiograms will be recorded 3 times at each time point. The individual mean at each time point will be calculated as raw parameters for descriptive analysis. The 12-lead ECG parameters (RR interval, PR interval, QRS interval, QT, QTcB, and QTcF) and change from Baseline (time-matched Baseline on Day -1) will be descriptively summarized at each time point by group. Baseline per time (0h, 0.5h, 1h, 2h, 3h, 6h) at Day -1 is defined as the value of the corresponding time-matched measurements of the ECG parameters. Frequency tables of values outside the normal ranges will be produced by group and time point.

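### The Day -1 ECG baseline is matched to Day 8 by clock time, but no Day -1 meal is set or recorded, so a meal effect could be confounded with padsevonil in the change from baseline

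*Protocol*

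**What the plan says.** **ECG timing.** Protocol 10.7.3 schedules a Day -1 (no exposure) series at times "intended to match as closely as possible the timing of the PK sampling series planned for Day 8" (anticipated peak exposure). Section 8.1.2 anchors the morning series to the clock, starting "approximately 0.5h prior to the expected time of the morning dose on Day 8" and continuing to 6 h after that expected time, with one further evening recording. Section 10.7.3 gives the purpose of the series: to assess whether ECG parameters, QT above all, change with exposure.

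**Analysis.** Protocol 12.4.3 uses the "time-matched Baseline on Day -1" and summarises changes descriptively by time point and group. SAP 3.3 (Table 3-1) and SAP 10.4.2 also define the ECG baseline by time, without a meal condition. SAP 10.4.2 counts participants by QTcF change, with limits at 30 and 60 ms. SAP 4.1 plans no covariate adjustment.

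**Meals.** Protocol 7.8.4 opens its meal rule with the Treatment Period: "study participants will complete a light meal 30min prior to each" morning dose. Section 7.2 describes the same meal differently: "30 minutes after a light or standard meal for the morning dose". Beyond the dosing meals, "Study participants should keep their usual diet". The only fasting rule, in section 10.6, concerns laboratory tests: "Laboratory safety measurements will be performed after a fasting period of at least 4 hours only" at Screening. The Day -1 visit list in 8.1.2 contains no meal.

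**The concern.** A time-matched baseline is meant to remove variation that has nothing to do with the drug. It does so only if the conditions that move the ECG are alike at the same clock time on both days. Posture and replication are covered, since supine rest applies throughout and "All ECG recordings will be performed in triplicate". Food is not covered: on Day 8 the time since the last meal is fixed by the dosing rule, and on Day -1 it is left open.

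The plan has no means of separating the two afterwards. Both groups take padsevonil, there is no placebo arm, and no Day -1 meal times are collected that an analyst could adjust for. If fed state differs between the no-exposure day and the peak-exposure day, meal and exposure move together in the comparison that the ECG series was added to support. The study is multicentre, so Day -1 practice may also differ between units.

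**Working it through.** The plan states no figure for the ECG analysis. Its one power figure (about 92%, protocol 12.8) concerns AUCτ and does not depend on the ECG baseline. It reproduces: log-scale SD = √ln(1 + 0.5²) = 0.4724, difference = ln 1.75 = 0.5596, 14 per group, one-sided 0.05, noncentral t with 26 df, giving 92.0%.

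**Step 1. Time since the meal.** On Day 8 the morning meal is completed 0.5 h before the dose (7.8.4), so time since the meal = time since the dose + 0.5 h.

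| ECG relative to morning dose | Day 8, time after meal | Day -1, time after meal |
|---|---|---|
| about 0.5 h before | about 0 h | undefined |
| 0.5 h | 1.0 h | undefined |
| 1 h | 1.5 h | undefined |
| 2 h | 2.5 h | undefined |
| 3 h | 3.5 h | undefined |
| 6 h | 6.5 h | undefined |

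The Day 8 pre-evening ECG, about 0.5 h before the evening dose, falls around the end of the evening meal. A meal effect could therefore differ from one time point to the next.

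**Step 2. Bias at one time point.** Let d be the drug effect, m the effect of the Day 8 meal at that time, and f the share of participants who ate a comparable meal at the same clock time on Day -1. Assume that the others carry no meal effect on Day -1.

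Mean change = (d + m) - f × m = d + m × (1 - f), so the bias is m × (1 - f).

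Neither m nor f is in the documents. For an assumed m of -10 to +10 ms:

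- f = 0: bias -10 to +10 ms
- f = 0.5: bias -5 to +5 ms
- f = 1: bias 0

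**Step 3. Between groups.** The difference in mean change is (d₁ - d₂) - m × (f₁ - f₂). Both groups follow the same rules, so there is no systematic reason for f₁ to differ from f₂, and the second term drops out.

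**Step 4. Category counts, for illustration only.** Suppose that the drug does nothing and that individual QTcF changes are normal around the bias b. The chance of a change of at least 30 ms at one time point is 1 - Φ((30 - b)/SD). The SD is also assumed.

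| b (ms) | SD 10 ms | SD 15 ms |
|---|---|---|
| -10 | under 0.01% | 0.38% |
| -5 | 0.02% | 0.98% |
| 0 | 0.13% | 2.28% |
| +5 | 0.62% | 4.78% |
| +10 | 2.28% | 9.12% |

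In a group of 14, the largest contrast (SD 15, b from 0 to +10) is 14 × 0.0912 - 14 × 0.0228 = 1.28 - 0.32 = 0.96, or about one participant at a time point. A negative b would hide changes instead.

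**The case against.** The strongest reply is that the documents show an unspecified meal and not a different one. Nobody is told to fast on Day -1, and the usual-diet sentence is not worded as limited to the Treatment Period. The comparison may well be fed against fed. This stands. A reader might infer that participants are unfed on Day -1 and that the ECG means are therefore biased by the full meal effect. That would need f = 0, which no section supports.

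Second, no section says that a meal moves QTcF, by how much or in which direction. This also stands, and the ranges above are assumptions.

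Third, a shift common to both groups cancels in the between-group contrast. If OXC lowers padsevonil exposure, as the sample-size section assumes (43% lower AUCτ), an exposure-driven ECG effect would tend to differ by group while a shared meal shift would not. This gives the contrast some use in separating the two. It does not repair the within-group changes, which are what the plan summarises.

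Fourth, ECG changes are other safety variables, analysed descriptively. SAP 10.4.2 also tabulates observed QTcF, which needs no baseline, and other day-to-day differences would remain without a placebo arm. All of this limits the importance of the point. It does not answer it, because the missing meal condition cannot be recovered once Day -1 has passed.

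Fifth, the low cost depends on participants being in the unit on the morning of Day -1. Protocol 5.2.1.2, 8.1.2 and the Table 5-1 notes have them check in the afternoon before. SAP 3.2.2 puts check-in on Day -1, and protocol 10.6 speaks of tests before admission on Day -1. These passages need to be aligned.

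**Conclusion.** The point holds as a gap in the design of the baseline day. The ECG baseline is matched on clock time, posture and replication, but not on food. A meal effect could therefore be confounded with padsevonil in the within-group change from baseline and in the exposure-ECG evaluation.

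The size is m × (1 - f) at each time point. It is the whole meal effect if nobody ate comparably on Day -1 and nothing if every unit happened to serve a matching meal. The formula assumes that participants without a comparable Day -1 meal carry no meal effect at that time. Direction and magnitude are unknown from the documents.

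Two further inferences should be avoided. The OXC-versus-control contrast is not systematically biased, because both groups follow the same rules. Nor is the Day 8 morning meal a fixed standard meal, because 7.8.4 calls it light while 7.2 allows light or standard. The primary PK analysis and its power are unaffected.

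**What to change.** - In protocol 7.8.4 and 8.1.2, require on Day -1 the same type of morning meal as on Day 8, completed 30 min before the expected Day 8 dosing clock time. Keep later meals at the same clock times on both days up to the last matched ECG, and record meal times on both days.
- Reconcile the description of the morning meal in 7.8.4 with that in 7.2, so that the Day 8 condition to be matched is defined.
- Align the Day -1 check-in wording in protocol 10.6 and SAP 3.2.2 with protocol 8.1.2.

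The cost is a short protocol addition, a meal for participants whom 8.1.2 already places in the unit, and slightly tighter Day -1 logistics. No dose, visit or analysis model changes.

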11.1 Adherence to protocol

The Investigator should not deviate from the protocol. However, the Investigator should take any measure necessary in deviation from or not defined by the protocol in order to protect clinical study participants from any immediate hazard to their health and safety. In this case, this action should be taken immediately, without prior notification of the regulatory authority, IEC, or sponsor.

After implementation of such measure, the Investigator must notify the EPM of the sponsor within 24 hours and follow any local regulatory requirements.

11.2 Monitoring

Monitoring of the study will be delegated by UCB to a CRO. The CRO will monitor the study to meet the CRO's monitoring SOPs, ICH-GCP guideline, and applicable regulatory requirements, and to ensure that study initiation, conduct, and closure are adequate.

The Investigator and his/her staff are expected to cooperate with UCB (or designee) and to be available during the monitoring visits to answer questions sufficiently and to provide any missing information. The Investigator(s)/institution(s) will permit direct access to source data/documents for study-related monitoring, audits, IEC review, and regulatory inspection(s).

The Investigator will allow UCB (or designee) to periodically review all eCRFs and corresponding source documents (eg, hospital and laboratory records for each study participant). Monitoring visits will provide UCB (or designee) with the opportunity to evaluate the progress of the study, verify the accuracy and completeness of eCRFs, ensure that all protocol requirements, applicable authorities regulations, and Investigator's obligations are being fulfilled, and resolve any inconsistencies in the study records.

11.Ž.1 Definition of source data

All source documents must be accurate, clear, unambiguous, permanent, and capable of being audited. They should be made using some permanent form of recording (ink, typing, printing, optical disc). They should not be obscured by correction fluid or have temporary attachments (such as removable self-stick notes).

Source documents are original records in which raw data are first recorded. These may include hospital/clinic/general practitioner records, charts, diaries, x-rays, laboratory results, printouts, pharmacy records, care records, ECG or other printouts, completed scales, quality of life

Source documents that are computer generated and stored electronically must be printed for review by the monitor (eg, ECG reports). Once printed, these copies should be signed and dated by the Investigator and become a permanent part of the study participant's source documenta The Investigator will facilitate the process for enabling the monitor

Electronic data records, such as Holter monitor records or electroencephalogram records, must etter be saved and stored as instructed by UCB (or designee).

